2.3.2 Known Potential Benefits

The first study, published in 1986, compared 16 ARDS patients treated with intravenous vitamin C (1000 mg intravenous every 6 hours) plus antioxidants (N-acetylcysteine, selenium, and vitamin E) to 16 ARDS patients who received the standard care at that time (i.e., control group). There was a significant reduction in mortality in the vitamin C group: 37% versus 71% in the standard care group ($p<0.01$). (12) A phase I trial in 2014 revealed that plasma vitamin C levels in patients with severe sepsis and *ARDS were low, almost at scorbutic levels* (13). HDIVC administration (200 mg/kg/day) raised plasma levels up to 3,000 μ M by day 4 and had a dose-dependent effect in the prevention of multi-organ failure, as measured by the Sequential Organ Failure Assessment (SOFA) scores. (14) As mentioned above, our Phase 2 double-blind, placebo-control multicenter randomized control trial (CITRIS-ALI, 11) also suggested that 200mg/kg/day of HDIVC (administered in 50 mg/kg/dose, every 6 hours) reduces the extent of organ failure (figure) and reduces 28-day and 60-day mortality in ARDS. Finally, ongoing treatment in China suggests that HDIVC may be effective in preventing ARDS in patients with COVID-19. The results of CITRIS-ALI suggested that the **Number Needed to Treat (NNT) is approximately six to save on human life.**

2.3.3 Assessment of Potential Risks and Benefits

The identifiable risks arising from exposure to the intravenous ascorbic acid infusion are low. Due to the severity of COVID-19, the study related risks associated with the study procedures

are not greater than the risks associated with hospitalization due to COVID-19. Given the low risk associated with the study and the potential high likelihood of benefit, we assess the risk/benefit ratio to be low (i.e., that benefit far outweighs risk).

3 - Objectives and Endpoints

3.1 Objectives and Endpoints

OBJECTIVES	ENDPOINTS	JUSTIFICATION FOR ENDPOINTS
Primary		
WHO COVID-19 9-point Ordinal Scale Outcome	MEAN SCORE ON DAY 28, 60 AND 90	This ordinal scale captures a range of safety outcomes and is ideal for safety studies. If any other unanticipated clinical harms of high-dose intravenous vitamin C occur, will be captured on this outcome.
Secondary		
Renal safety biomarkers	Daily serum oxalate Daily urinalysis 24-hour urine oxalate on day 5	Measured biomarkers will provide a sensitive way to identify the mechanisms of oxalate nephropathy
AKI-free days at day 28 and 90	Renal-failure free days, with AKI defined by the KDIGO criteria (see table below).	This endpoint aims to identify long-term kidney outcomes among the two groups
All-cause mortality at 28 60 and 90 days	Safety Endpoint	If the therapy offers significant benefit, or harm, compared with placebo
Exploratory biomarkers	Ferritin, D-dimer, LDH, CRP, plasma IL-6 on day 7	The biomarkers aim to help interpret the outcomes, and further explain clinical differences in the above-measured outcomes
Ascorbate trough levels	Plasma ascorbate at baseline (0 hours) levels at 24 hours, 48 hours, 96 hours and 168 hours	The PK of ascorbate is still unknown in the target patient population
Alive and free of significant respiratory failure through 28-days	At 28-days is the patient alive and not in respiratory failure, the principal cause of death by COVID-19	Respiratory failure defined as at least one of the following: 
 • Endotracheal intubation and mechanical ventilation • •Oxygen delivered by high-flow nasal

		
cannula (heated, humidified)
 
 • Oxygen delivered via reinforced nasal cannula at flow rates >20L/min with fraction of delivered oxygen ≥ 0.5) • Noninvasive positive pressure ventilation (CPAP or BIPAP) • Extracorporeal membrane oxygenation (ECMO of any type)

Alive and free of mechanical ventilation at 28-days
	
Proportion of patients alive and free of invasive mechanical ventilation at 28-days.
	
Is the patient dependent on mechanical ventilation by 28-days, that is development of significant chronic respiratory failure

WHO COVID-19, 9-point Ordinal Outcome Scale		
Patient State	Descriptor	Score
Uninfected	No clinical or virologic evidence of infection	0
Ambulatory	No limitation of activities	1
	Limitation of Activities	2
Hospitalized mild disease	Hospitalized, no oxygen therapy	3
	Oxygen by mask or nasal prongs	4
Hospitalized Severe Disease	Non-invasive ventilation or high-flow oxygen	5
	Intubation and mechanical ventilation	6
	Ventilation + additional organ support – vasopressors, renal replacement therapy, ECMO	7
Dead	Death	8

Acute Kidney Injury (AKI) Definitions per KDIGO guidelines

Khwaja, A. (2012). KDIGO clinical practice guidelines for acute kidney injury. *Nephron Clinical Practice*, 120(4), c179-c184.

Stage	Serum creatinine	Urine output
1	1.5–1.9 times baseline OR ≥0.3 mg/dl ($\geq 26.5 \mu\text{mol/l}$) increase	<0.5 ml/kg/h for 6–12 hours
2	2.0–2.9 times baseline	<0.5 ml/kg/h for ≥12 hours
3	3.0 times baseline OR Increase in serum creatinine to ≥4.0 mg/dl ($\geq 353.6 \mu\text{mol/l}$) OR Initiation of renal replacement therapy OR, In patients <18 years, decrease in eGFR to <35 ml/min per 1.73 m ²	<0.3 ml/kg/h for ≥24 hours OR Anuria for ≥12 hours

4 - Study Design

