CLINICAL STUDY PROTOCOL

C. Kenneth and Dianne Wright
Center for Clinical and Translational Research

SAFEty Study of Early Infusion of Vitamin C for Treatment of Novel Coronavirus Acute Lung Injury

(SAFE EVICT CORONA-ALI)

Protocol Version: 1.83

Protocol Version IRB approved: 08/10/2021

VCU IRB Number: HM20018977

ClinicalTrials.gov Identifier: NCT04344184

IND: 149518

Study Personnel

Principal Investigator(s) [name]
Virginia Commonwealth University
Department of Internal Medicine
Pulmonary and Critical Care Medicine

[name], MD
Virginia Commonwealth University
Department of Internal Medicine
Pulmonary and Critical Care Medicine

Co-Investigators
[name]
Central Virginia VA Health System
Department of Internal Medicine
Gastroenterology and Hepatology Division

[name]
Department of Biostatistics
Virginia Commonwealth University,
Massey Cancer Institute

[name]
Virginia Commonwealth University
Department of Surgery
Division of Trauma Surgery

[name]
Virginia Commonwealth University
Department of Surgery
Division of Trauma Surgery

Clinical Coordinators: [name] and [name]
Virginia Commonwealth University
Department of Internal Medicine
Pulmonary and Critical Care Medicine

Regulatory Contact: [name]
Virginia Commonwealth University
Department of Internal Medicine
Pulmonary and Critical Care Medicine

Synopsis

Study Description

The purpose of this proof-of-concept, phase 2 safety study is to examine the safety profile, and possible therapeutic effects of high-dose, intravenous vitamin C (HDIVC) compared to placebo in hospitalized adult patients with novel Coronavirus COVID-19 and hypoxemia.

Objectives

To assess the safety profile of a 4-day (96-hour) intravenous vitamin C treatment protocol (comprised of four intravenous infusions a day, that is 50 mg/kg every 6 hours) in patients with laboratory-confirmed SARS-CoV-2 infection manifesting COVID-19 (Novel Coronavirus Disease 2019) with hypoxemia. While performing this phase 2 proof-of-concept, safety study, we will explore the following hypotheses:

Endpoint

Primary Endpoint (Safety): HDIVC infusion does not worsen the patients' outcomes, as measured by differences in the mean 9-point (from 0 to 8) World Health Organization (WHO) ordinal scale for disease improvement, between the two populations at 28, 60 and 90 days:

Table 1.

Patient State	Descriptor	Score
Uninfected	No clinical or virologic evidence of infection	0
Ambulatory	No limitation of activities	1

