8.3.6 Adverse Events, Serious Adverse Events, and Unanticipated Problems

Adverse events (AEs), serious adverse events (SAEs), and unanticipated problems (UPs) occurring at VCU will be managed and reported in accordance with [VCU/VCUHS Clinical Research Standard Operating Procedures #CR-RE-300.1: Adverse Event Management and Reporting](#). Those occurring at the VA will be managed and reported in accordance with the VA's standard operating procedures.

All serious adverse events (SAEs) will be followed until a satisfactory resolution or until the site investigator deems the event to be chronic or the participant is stable.

The PI/sponsor will be responsible for notifying the Food and Drug Administration (FDA) of any unexpected fatal or life-threatening suspected adverse reaction as soon as possible, but in no case later than 7 calendar days after being informed about the event. In addition, the PI/sponsor must notify FDA and all participating investigators in an Investigational New Drug (IND) safety report of potentially serious risks, from clinical trials or any other source, as soon as possible, but in no case later than 15 calendar days after the PI/sponsor determines that the information qualifies for reporting.

[figure not shown]
9 - Statistical Considerations

[figure not shown]
[figure not shown]
Model Set-Up:

We plan to use a two-sample, unequal-variance 2-tail t-test for comparing the mean differences between the two groups, the vitamin C arm and placebo arm. The actual interventions will be blinded and will be revealed after the completion of statistical analysis, therefore, we will be labeled as group A and group B. No one besides the DSMB and independent statistician supporting the DSMB will have access to the comparative data, even if the treatment groups are masked as group A and Group B.

[figure not shown]
This is a proof-of-concept study, **with predetermined sample sizes** for each arm, which is 30 patients for group A and 30 patients for group B, therefore the **power analysis is driven by the predetermined sample size and did not determine the sample size.**

[figure not shown]

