Therefore, this proof-of-concept study of 60 patients, 30 allocated to the treatment arm and 30 to the placebo arm, will have 96% power (1-beta (β)) to detect an **average of 1-point difference** in the primary outcome, the WHO COVID-19 ordinal scale, with an alpha error probability (α) of 4% (0.04). This is by applying a two-tail, t-test with unequal variances (see figure below).

[figure not shown]

For binary secondary outcomes, we plan to use the chi-squared test, with 1-degree of freedom. The expected effect size for an alpha level of 0.05 and power of 80% is 0.36, as shown in the figure below.

In contrast, for a constant hypothetical effect size of 0.2, a phase 3 trial will require at least 200 patients to achieve a power of 80% and an alpha of 0.05 (yellow line, figure below).

Planned Interim Analyses:

No planned interim analyses will be conducted in this study. The results will be analyzed after the 60th patient has finished enrollment and has been discharged from the hospital (phase 1). There are no provisions to stop the trial early for efficacy.

Missing Data

The primary outcome, the WHO-COVID-19 scale is encompassing missing data from death or hospital discharge. Missing laboratory or clinical data due to patient death, or discharge will not be imputed given this practice will introduce systematic bias, since they are not missing at-random. For organ-system data, the highest scores will be attributed after patient death, since death causes cessation of all organ function, and any imputation method will underestimate the severity. For missing-at-random data, multiple imputation with a pattern-mixture model with control-based pattern imputation will be used, with 50 imputed data sets, in order to compensate for data that may be missing at random.

10 - Supporting Documentation and Operational Considerations

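### The primary endpoint names three days, but Section 9 does not say which day or combination rule its 4% alpha and 96% power refer to, and the analysis trigger can precede those days

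*Combined protocol and SAP*

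**What the plan says.** Section 3.1 gives the primary endpoint as "MEAN SCORE ON DAY 28, 60 AND 90". The synopsis likewise defines it through differences in mean WHO score "between the two populations at 28, 60 and 90 days". Neither place ranks the days.

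Section 9 describes one analysis: "We plan to use a two-sample, unequal-variance 2-tail t-test for comparing the mean differences between the two groups". The power statement, for "30 allocated to the treatment arm and 30 to the placebo arm", is that the study "will have 96% power (1-beta (β)) to detect an" "average of 1-point difference" "with an alpha error probability (α) of 4% (0.04". No day is attached to the difference, the alpha or the power. The available text contains no primary day, testing order, alpha split, any-day or all-days rule, or repeated-measures model.

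On timing, Section 9 (Planned Interim Analyses) says: "The results will be analyzed after the 60th patient has finished enrollment and has been discharged from the hospital (phase 1". The synopsis (Study Duration) has phase 1 ending on day 28 and phase 2 at the 90-day follow-up.

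**The concern.** One alpha and one power describe one test. Attached to an endpoint with three time points, they have no defined meaning until the plan says which test or rule they belong to. If a difference on any day counts, there are three chances of a false signal. If all three days must agree, power is below the single-test figure, and harm confined to day 28 would not count. The trial's primary question is whether the infusion worsens outcome, and Section 10.1.2 lists unacceptable risk on the primary outcome as a ground for suspension. It should therefore be clear in advance what result would count as such a signal.

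The trigger is a separate difficulty. It is tied to discharge, whereas the endpoint is tied to fixed days, so the analysis could start with scores missing simply because those days have not arrived.

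**Working it through.** **Inputs.** From Section 9: 30 per arm, a 1-point difference, two-sided alpha 0.04, power 96%. From the synopsis and Section 3.1: three days. Assumed: the SD of the score, which the available text does not give (the power figure is not shown), and the correlation between days.

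**1. The plan's own figure, for one test.** With SD = 1, the standardised shift is 1 × √(30/2) = 3.873. The two-sided 4% critical value is 2.054. Normal approximation: Φ(3.873 − 2.054) = Φ(1.819) = 96.6%. The noncentral t with 58 degrees of freedom gives 96.0%. The stated 96% is therefore a single-comparison figure if the SD is 1.0. Because that SD was back-solved from the 96%, the match does not confirm it independently. With the t-test, single-test power is 83.8% at SD 1.25, 68.5% at SD 1.5 and 43.9% at SD 2.

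**2. Three tests at 4%, independent days.**
- Any day counts: error = 1 − 0.96³ = 1 − 0.8847 = 11.5%.
- All days required: power = 0.96³ = 88.5%.

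**3. Three tests at 4%, correlated days.** Simulation of three Welch t-tests, 30 per arm, with the SD set to give 96% per test (about 1.0) and a common correlation (60,000 null trials; 40,000 with a 1-point effect on every day):

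| Correlation | Any day counts: error | All days required: power |
|---|---|---|
| 0 | 11.5% | 88.5% |
| 0.5 | 10.2% | 90.2% |
| 0.7 | 8.8% | 91.9% |
| 0.8 | 7.9% | 92.5% |
| 0.9 | 6.9% | 93.5% |
| 0.95 | 6.0% | 94.2% |

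A separate run of 2,000,000 trivariate normal draws gave errors of 8.9%, 8.0% and 6.8% and joint powers of 91.6%, 92.4% and 93.5% at correlations 0.7, 0.8 and 0.9. Under the all-days rule, error stays below 4% at every correlation in the table.

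**4. Rules under which 4% and 96% do hold together.**
- One named day: step 1.
- A fixed sequence: alpha stays at 4%, and power for the first day is the single-test 96%.
- Bonferroni with an any-day rule (0.04/3 = 0.0133 per day) and the effect present on all days: error at most 4%, power 99.9% at correlation 0, 98.5% at 0.5, 96.1% at 0.8, 94.6% at 0.9 and 93.3% at 0.95. Power on any one given day is then 90.2%.

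**5. Timing.** Suppose, as an illustration, that the 60th patient goes home on day 10. The trigger is met then, 28 − 10 = 18 days before the day-28 score and 90 − 10 = 80 days before the day-90 score.

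**The case against.** The best defence is that day 28 is already implied. Phase 1 ends on day 28, Section 4.1 puts days 60 and 90 in a second phase, and the analysis is tagged as phase 1. Section 4.4 and the synopsis (End of Study Definition) call the 90-day outcomes secondary. The Schedule of Activities leaves the WHO scale blank at days 60 and 90, although one of two WHO rows in the Section 8.1.1 schedule marks it. This reading is plausible and supports the proposed fix. It does not remove the point, because both definitions of the primary endpoint list all three days equally.

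A reader might infer that 4% alpha and 96% power cannot both be true. The documents do not support that. Step 4 gives several rules under which both hold. Nor do the documents say that three separate tests will be run; Section 9 describes one t-test, and three tests is an inference from the endpoint definition.

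A reader might also infer that day 60 and 90 scores will be collected with arms known. Section 9 has the arms revealed once the statistical analysis is complete, which may mean all analysis, and restricts comparative data to the DSMB and its independent statistician. Early unblinding is possible under the wording but is not stated.

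It is fair to add that in a small safety study a missed harm costs more than a false alarm. Any-day testing at 4% per day gives 97-100% power for a 1-point effect present on all days, and the all-days loss is modest. Independence is also implausible, since death scores 8 and persists. These points limit the size of the problem. They do not tell the reader which rule applies.

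**Conclusion.** The point holds as a gap in definition: the plan does not attach its alpha and power to a day or a rule, so overall error and power are undefined for the endpoint as written. If each day were tested at 4% and any day counted, error would be about 6-9% at correlations of 0.95 to 0.7, with 11.5% as the independence figure. If all days were required, power would be about 92-94%, with 88.5% under independence. The correlations and the 1-point SD are assumptions. The SD matters more than the multiplicity: at SD 2 even the single test has 43.9% power.

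The timing defect stands on its own: read literally, the trigger can precede the very scores to be analysed.

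The plan should be changed on both counts. Confidence is moderate, since several Section 9 figures are not shown and could state the SD or a day.

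**What to change.** In the synopsis, Section 3.1 and Section 9, name day 28 as the single primary time point to which the 4% alpha and 96% power apply, and state the SD behind the 96%. Report days 60 and 90 as secondary, with estimates and confidence intervals. A prespecified fixed sequence starting at day 28 would also keep alpha at 4%.

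Change the trigger to the point at which the 60th patient has reached day 28. Moving the trigger alone does not protect the later scores, so also state that arms stay masked to outcome assessors until day-90 data are complete.

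Align the schedules with this choice. The Schedule of Activities collects the WHO score after day 7 only while the patient is in hospital, so it should say how day 28 is scored after discharge.

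The cost is a small amendment needing IRB approval. Days 60 and 90 lose primary status, and the analysis may wait up to 28 days after the last enrolment. With one primary day, the sample size need not change on multiplicity grounds. By comparison, a Bonferroni split that kept 96% power on each day would need about 38 per arm at SD 1.

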4.1 Overall Design

1. A phase 2, two-center, prospective, randomized, double blind placebo-controlled safety clinical trial.
2. A maximum of 60 patients will be enrolled.
3. Participants will be randomized to receive either intravenous Vitamin C (mixed in 5% dextrose in water) or placebo (5% dextrose in water) in a 1:1 manner.
4. Active treatment will continue for 96-hour period or consent withdrawal or loss to follow-up. One-fourth of the 24-hour calculated dosage will be administered **in 30-minute intravenous infusions of 50 mg/kg and occur every 6 hours** for a total of sixteen 30-minute infusions. **That is 200 mg/kg total per day for 4 days.** The standard of care therapy will be followed. All COVID-19 known therapies will be allowed.
5. All participants will be followed for a total of 28 days on the first phase of the trial and at 60 and 90 days on the second phase.
6. All participants, without exception, will receive the standard of care for COVID-19 including the use of remdesivir, dexamethasone, plasma and other, as a component of standard of care for patients hospitalized with severe disease, in settings where remdesivir is available via the emergency use authorization mechanism.

Analysis/Interim Monitoring:

1. **Only reasons for study withdrawal are withdrawal of consent and, or loss to follow-up**
2. The DSMB will review all SAEs in a narrative and qualitative fashion (not only quantitative), to avoid underpowered statistical misconceptions.
3. Protocol compliance will be monitored by the study team daily discussion. This will take place via investigator conference call and will address challenges encountered. Trial progress will be monitored by an independent Data and Safety Monitoring Board (DSMB) to determine if the study should stop for safety reasons.

4.2 Scientific Rationale for Study Design

The purpose of this study is to assess the safety, tolerability, efficacy of intravenously infused ascorbic acid therapy for patients with COVID19 and decreased oxygenation. **This study will provide an opportunity to explore specifically the specific safety of high-dose intravenous vitamin c and explore the hypothesis generated by case reports, that high-dose vitamin C has clinically significant adverse effects on the kidneys.** By administering the infusion at the first objective sign of worsening oxygenation, documented by Pulse Oximetry Saturation(SpO₂)/Fraction of Inspired Oxygen (FiO₂) – that is the S/F ratio, decreased pulse oximetry at baseline, HDIVC may reduce the inflammatory process and development of respiratory failure requiring intubation, which is critical in a pandemic when ventilators, ICU beds, and medical staff may be in short supply.

4.3 Justification for Dose

Dosing and bio-distribution data in humans show that pharmacological concentrations of vitamin C can only be attained following intravenous administration. (29) Oral doses cannot achieve therapeutic plasma concentrations. (34-35) Dosage selection for this trial was determined both from animal modeling, examining the biological effectiveness in a lung injury model system and from the recently conducted randomized double-blind phase 2 human ARDS (CITRIS-ALI) trial. (11) **The 200 mg/kg/24-hour IV (50 mg/kg IV every 6 hours)** dosing protocol was determined from analysis of the CITRIS-ALI (200mg/kg IV levels, that was 50 mg/kg IV every 6 hours) plasma ascorbate levels. **A special consideration is given for patients who will develop KDIGO definition AKI, stage 2 or 3 after the infusion. In this scenario, the dosage will be reduce by 50%, for each subsequent**

infusion, until the AKI resolves completely. We are using a dosing ceiling of 15 grams per day, for consideration of vitamin C dosages in obese population. Under no circumstance an individual infusion dose will exceed 3.75 grams of vitamin C, or the daily infused dose above 15 grams.

4.4 End of Study Definition

Active treatment period will continue for 4 days, that is 16 infusions of 50 mg/kg intravenous vitamin C, 30-minutes each infusion. The last study-specific bloodwork will be collected at 7 days. **All patients will remain in the study through the end of double-blind period and final study blood collection.** Participation will end if patient withdraws the consent or is lost to follow-up. Clinical data, including a final blood draw, will be collected through day 7. All subjects will be followed to day 28 via chart review for collection of clinical outcomes data. 90-day secondary outcomes will be assessed either during clinic visits or via telephone at 60 and 90 days. **Only acceptable reasons for early study termination include consent withdrawal, or loss to follow-up.**

5 - Study Population

